6 GENERAL PRINCIPLES

6.1 General

The Full Analysis Set will be used for all the safety analyses and efficacy analyses except endpoints of DOR and TTR, which will be conducted on the subjects in the full analysis set with an objective response (CR or PR). Some analyses may be repeated in the selected subgroups specified in Section 4.3 depending on data availability.

Unless otherwise specified, all continuous variables will be summarized using descriptive statistics, which will include the number of subjects with a valid measurement (n), mean, standard deviation (SD), median, 25% quantile (Q1), 75% quantile (Q3), minimum and maximum. All categorical variables will be summarized using frequencies and percentages. The exact binomial 2-sided 95% confidence interval (CI) will be provided for all binary efficacy endpoints, including ORR and DRR. Kaplan-Meier (K-M) estimates along with their corresponding 95% CI will be calculated for time-to-event endpoints.

The following terms may be used for this SAP and tables, figures and listings (TFLs):

- **Study treatment:** Study treatment refers to all the protocol specified treatment administered to subjects.
- **Enrolled subjects:** refers to subjects who receive study treatment.
- **Enrollment date:** refers to the date that the informed consent form was signed.
- **Study day:** The subject's time on study will be determined in study days. Day 1 is defined as the day of the first study treatment administration. Study day is defined as the date of interest minus day 1 plus 1 if the date is on or after day 1. If the date is before day 1, the study day is defined as the date of interest minus day 1.
- **Baseline:** refers to day 1 prior to the first administration of study treatment. The baseline value of a parameter (eg, laboratory tests and efficacy endpoints) is defined as the last value prior to the first study treatment administration.
- **Duration of treatment:** defined as the date of the last dose of study treatment minus the date of the first dose of study treatment + 1
- **Treatment exposure period:** from day 1 through 30 days after the last administration of study treatment.
- **Restriction Switch:** Subjects could change to tabelecleucel with a different HLA restriction from a different donor either due to a lack of efficacy from the current cell line or insufficient supply. "Restriction switch" refers to only the change to tabelecleucel with a different HLA restriction due to lack of efficacy.
- **Year:** A year consists of 365.25 days
- **Month:** A month consists of 365.25/12 days

6.2 Missing Data Handling

In general, missing data will not be imputed. Only year of birth was collected during the study. To calculate age, 01 July was used to impute the birthday and month.

6.3 Visit Window

Depending on the statistical analysis method, single values may be required for each analysis window. For example, change from baseline by visit usually requires a single value per visit. When a single value is needed, the following rule(s) will be used:

- In general, the baseline value will be the last non-missing value on or prior to the date of the first dose of study treatment, unless specified differently.
- For post-baseline visits, if there are multiple assessments in a same visit window, the assessment closest to the corresponding dose date will be used in the analysis. For example, if after cycle 1 day 1 (first infusion) lab samples are collected on day 3 and day 5 before cycle 1 day 8 (second infusion), the lab assessment collected on day 3 will be used for cycle 1 day 1.

For summary of laboratory data by visit window, it is possible that large time gaps exist between dosing cycles. To account for this, a cycle is defined to start at the first dose of the cycle and end at the first dose of the next cycle or first dose of the cycle + 50 days, whichever is earlier. For the last cycle, the cycle ends at first dose of the cycle + 50 days or last dose of the cycle + 30 days, whichever is earlier. Within a cycle, additional visits may be defined based on the actual infusion date of each dose. The window of an infusion visit starts at the infusion date and ends at the day before the next infusion date. If an infusion is the last infusion for a cycle, the infusion visit window ends at the day before the start of next cycle or the infusion date + 27 days, whichever is earlier.

Disease assessments performed by investigator will be grouped into one visit if the gap between two consecutive assessments is less than or equal to 14 days.

6.4 Data Handling and Electronic Transfer of Data

Analysis Data Model (ADaM) data sets will be prepared for statistical analysis. ADaM data are derived from the Study Data Tabulation Model (SDTM) data. SDTM data are derived from raw data entered into the clinical trial database.

Data files were provided from the site via secured transfer. The data was mapped from the raw files to the fields available in the clinical trial database. The formatting of the data into data entry packets was done in accordance with Atara Work Instruction. The data was then transferred via secured server to the vendor for entry into the trial database using the vendor's standard operating procedures and data entry conventions.

6.5 Validation of Statistical Analysis

The statistical analysis validation procedure will be conducted in accordance with Atara's standard operating procedures (SOPs).

7 STUDY SUBJECTS

7.1 Study Disposition

Subject disposition, including the number of subjects screened, the number of subjects deemed eligible and the number of subjects enrolled/treated, will be summarized. Treatment status (completed or discontinued) with reasons for treatment discontinuation and end of study status (completed or discontinued) with reasons for not completing the study will also be summarized. The analysis will be repeated for the subgroups defined in Section 4.3.

7.2 Important Protocol Deviations

Important protocol deviations (IPDs) will be reviewed prior to the final database lock. A by-subject listing of IPDs will be provided, which will include IPD category, subcategory.

7.3 Demographic and Baseline Characteristics

The following demographic and baseline characteristics for full analysis set and the subgroups defined in Section 4.3 will be summarized using descriptive statistics. Baseline weight will be defined as the last screening weight.

- Age at baseline: descriptive statistics and n (%) for the following:
 - < 2, 2 to < 12, 12 to < 16, 16 to < 65, and ≥ 65 years
 - < 16 and ≥ 16 years
 - < 2, 2 to < 12, 12 to < 18, 18 to < 65, and ≥ 65 years
 - < 18 and ≥ 18 years
- Sex (male, female)
- Ethnicity (Hispanic, non-Hispanic)
- Race (White, Black or African American, Asian, Unknown)
- Time from initial diagnosis of EBV⁺ disorder to first dose of study treatment (months)
- Disease risk subgroups (for subjects ≥ 16 years and for subjects ≥ 18 years)
 - a) Age < 60 years (low risk), age ≥ 60 years
 - b) Serum lactate dehydrogenase (LDH) concentration: normal (low risk), elevated (> upper limit of normal [ULN])
Time from initial diagnosis to first dose of study treatment (months)

The following disease characteristics will be summarized for HCT and SOT subjects only:

- Central nervous system (CNS) disease
- Extranodal disease at baseline (including bone marrow [BM])
- Lymph node disease
- ≥ 3 sites of disease
- Time from transplant to diagnosis of EBV^+ PTLD

7.4 Extent of Exposure

Descriptive statistics will be provided for average number of weight-adjusted cells per dose (10^6 cells/kg), number of lots subjects received, number of treatment cycles, number of doses, and duration of treatment (date of last dose of tabelecleucel – date of first dose of tabelecleucel + 1). Summary and listing of the subjects who undergo Restriction Switch will also be provided.

The analysis will be repeated for the subgroups defined in Section 4.3

8 EFFICACY ANALYSES

For the primary efficacy analysis, all response assessment data will be included regardless of how many Restriction Switches the subjects had.

Efficacy analyses will be conducted by cohorts and combined cohorts, as specified in Section 4.2.

Disease assessments performed by investigators regardless of modalities will be grouped into one timepoint assessment if the gap between two consecutive disease assessments is less than or equal to 14 days. This grouping will continue for the same timepoint assessment until the gap between two consecutive disease assessments exceeds 14 days.

The ranking for assessment modalities is specified in Table 2. If there are multiple assessments with the same modality in the same timepoint assessment, the worst/worse assessment (from the best to the worst in the order of not evaluable [NE], CR, PR, stable disease [SD] and progressive disease [PD]) will be selected for that modality. If there are assessments based on multiple modalities for a timepoint assessment, then the overall response for the timepoint assessment will be decided by the rank of the modalities specified in Table 2. For example, for a timepoint assessment, a PR was assessed per biopsy and a CR was assessed per physical examination. The assessment per biopsy will override that of physical examination for this timepoint assessment. If PD is determined as the response for a timepoint assessment, the earliest assessment date among all the disease assessments for this timepoint assessment will be considered as the PD date. If SD, PR or CR is determined as the response for a time assessment, the latest assessment date among all the disease assessments for this timepoint assessment will be considered as the response date.

While in general if any therapy directed towards the disease being treated, other than protocol-specified treatment, is initiated, response data after the initiation date of such therapy may be censored. However, given the fact that some anti-underlying disease therapies were actually allowed per the protocol, in the primary analysis of disease assessment related endpoints, none of such therapies were considered for censoring rule. As a sensitivity analysis, response data after the initiation of such therapies are censored, and such analysis is conducted for the endpoints including ORR, DOR, and PFS based on the Full Analysis Set.

Table 2: Rank of the Modalities (1 indicates highest rank)

Modality	Priority for non-Viremia	Priority for Viremia
BIOPSY	1	1
PATHOLOGY	1	1
BONE MARROW	1	1
PET	2	2
PET SCAN	2	2
PET/CT SCAN	2	2
CT SCAN	2	2
MRI	2	2
ULTRASOUND	3	3
THALLIUM SCAN	4	4
PHYSICAL EXAM	4	4
BLOOD	4	1
CLINICAL LABS	4	4

Abbreviations: CT, computed tomography; MRI, magnetic resonance imaging; PET, positron emission tomography

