### **VIII. Post-Infusion Evaluation**

The evaluations below are approximate and will be performed as clinically necessary:

Patients will be evaluated by interval medical history and physical examination daily during the T-cell infusions. Vital signs will also be monitored prior to and at 1, 2, 4, and 24 hours following initiation of each infusion of EBV-specific T-cells. Thereafter, patients will be clinically evaluated at least weekly during the three week periods of observation following each course of infusions and, subsequently, at monthly intervals until 6 months post initial infusion. Patients achieving complete remission will be evaluated at six month intervals for one year thereafter, or more frequently as clinically indicated to assess duration of response. Patients achieving partial remissions or stable disease three weeks following the second course of T-cell infusions will be closely followed until first evidence of further progression, at which time alternative therapies may be initiated. Patients exhibiting disease progression within three weeks after the second course of T-cell infusions may also be considered for alternative treatments.

Patients will also be assessed for the effects of the adoptively transferred EBV-specific T-cells or circulating levels of EBV DNA. For these studies, heparinized blood (10cc) will be drawn on days 1, 7, 14, 21, and 28 post-T-cell infusion and, monthly thereafter for four months. Isolated PBMC will be assayed for EBV DNA copy number, using a standard quantitative PCR amplified assay, (59).

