4.2 Subject Cohorts

Analysis cohorts are defined based on subjects' disease background, prior EBV⁺ disease therapy, and source of study treatment received (as defined in Section 2.4). The cohort definitions are specified in [Table 1](#). With respect to prior EBV⁺ disease therapy, subjects with prior rituximab therapy data reported will be assigned to the relevant refractory/relapsed (R/R) rituximab cohort; subjects with no prior rituximab therapy data reported will be assigned to the rituximab-naïve cohort.

All analyses will be presented by the cohorts and combined cohorts defined in this SAP, not by the groups defined in the protocol. Cohorts to be used in the analysis depend on the data availability.

Table 1: Cohorts

Cohort Number	Cohort Name	Subjects Enrolled in The Study
1	Tab-cel HCT EBV ⁺ PTLD R/R Rituximab	Y
2	Tab-cel HCT EBV ⁺ PTLD Rituximab Naïve	Y
3	Tab-cel SOT EBV ⁺ PTLD R/R Rituximab	N
4	Tab-cel SOT EBV ⁺ PTLD R/R Rituximab + Chemo	Y
5	Tab-cel AID LPD	Y
6	Tab-cel PID LPD	Y
7	Tab-cel Lymphoma	N
31	Tab-cel LMS	Y
32	Tab-cel NPC	Y
61	Tab-cel Other Solid Tumor	N
71	Tab-cel Viremia	N
101	EBV-CTL (Transplant donor derived) HCT EBV ⁺ PTLD R/R Rituximab	Y
102	EBV-CTL (Transplant donor derived) HCT EBV ⁺ PTLD Rituximab Naïve	Y
103	EBV-CTL (Transplant donor derived) SOT EBV ⁺ PTLD	Y
106	EBV-CTL (Transplant donor derived) PID LPD	Y
107	EBV-CTL (Transplant donor derived) Lymphoma	Y
171	EBV-CTL (Transplant donor derived) Viremia	Y
201	Autologous	Y

Abbreviations: AID, acquired immunodeficiency; chemo, chemotherapy; CTL cytotoxic T lymphocyte; EBV, Epstein-Barr virus; HCT, hematopoietic cell transplant; LPD, lymphoproliferative disorder; N, no; NPC, nasopharyngeal carcinoma; PID primary immunodeficiency; post-transplant lymphoproliferative disorder; R/R, refractory/relapsed; SOT, solid organ transplant; tab-cel, tablecleucel; Y, yes

Disposition, demographics, baseline characteristics, exposure and safety will be summarized as in the following headers:

Table a: HCT Cohorts:

Tab-cel HCT EBV+ PTLD				EBV-CTL (Transplant donor derived)			Total (cohort 1, 2, 101, 102)
R/R	Rituximab	R/R	Rituximab	Naïve	Total		
Rituximab (cohort 1)	Naïve (cohort 2)	Total (cohort 1+2)	(cohort 101)	Naïve (cohort 102)	Total (cohort 101+102)		

Table b: *SOT Cohorts*:

Tab-cel SOT EBV+ PTLD R/R Rituximab+Chemo (cohort 4)	EBV-CTL (Transplant donor derived) SOT EBV+ PTLD (cohort 103)	Total (cohort 4+103)
--	---	-------------------------

Table c: *Other cohorts and All cohorts*:

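### Read literally, the SAP's timepoint rule lets a not-evaluable biopsy void an evaluable scan, and it sets no limit on how long a timepoint can run

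*SAP*

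**What the plan says.** SAP section 8 derives each timepoint response in steps.

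- **Grouping.** Assessments of any modality join while consecutive gaps are 14 days or less: "This grouping will continue for the same timepoint assessment until the gap between two consecutive disease assessments exceeds 14 days". SAP 6.3 repeats the rule: assessments "will be grouped into one visit if the gap between two consecutive assessments is less than or equal to 14 days". Neither place limits the total span.
- **Within a modality.** The worst result is taken, "from the best to the worst in the order of not evaluable [NE], CR, PR, stable disease [SD" and then PD. NE is at the best end, so it never displaces an evaluable result of the same modality.
- **Across modalities.** Here "the overall response for the timepoint assessment will be decided by the rank of the modalities specified in Table 2". Table 2 ranks biopsy, pathology and bone marrow 1; PET, CT and MRI 2; ultrasound 3; and physical exam and (outside viremia) blood 4. The one worked example, a biopsy PR over an exam CR, has two evaluable results.
- **Dating.** For PD, "the earliest assessment date among all the disease assessments for this timepoint assessment will be considered as the PD date". SD, PR and CR take the latest date in the timepoint. No date is given for a timepoint that resolves to NE.

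SAP 8.2.2 and 8.2.3 treat NE as not valid, but only in setting the censoring date and the 90-day death window.

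**The concern.** The authors dealt with NE inside a modality but not between modalities. As written, an uninformative biopsy outranks an informative scan and replaces it, whether the scan showed CR, PR, SD or PD. Separately, because a timepoint ends only at a gap of more than 14 days, closely spaced records can join two post-course evaluations into one. The highest-ranked modality then settles the merged timepoint, and the earliest or latest date is attached to it.

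This one derivation feeds the primary endpoint, ORR, and also DOR, PFS, DRR, TTP and TTR. A response or a progression can be lost, or dated weeks away from the assessment that showed it.

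**Working it through.** The plan gives no figure for this rule, so there is none to reproduce. I applied the rule literally to the protocol's schedule. The results placed on each day are assumed.

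**Inputs**
- Protocol, Treatment Plan VI: infusions on days 0, 7 and 14 (±3 days), then at least three weeks of observation. Back-to-back courses put course 2 on days 35, 42 and 49.
- Protocol, Treatment Plan VIII: imaging, if indicated, three weeks after each course and six weeks after the second. This gives 14 + 21 = day 35, 49 + 21 = day 70 and 49 + 42 = day 91.
- Same section: biopsy, if indicated, 2–3 weeks after the first and/or second dose (read here as infusion).
- SAP 6.1: a month is 365.25/12 days. SAP 8.2.4: a durable response lasts more than 6 months.

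**Step 1: NE within and across modalities**

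| Assessments | Rule as written | NE excluded first |
|---|---|---|
| CT PR day 35, CT NE day 40 | PR | PR |
| Biopsy NE day 28, CT CR day 35 | NE | CR |
| Biopsy NE day 28, CT PD day 35 | NE | PD |

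The fault arises only across modalities.

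**Step 2: can a biopsy and the day-35 scan share a timepoint?** After infusion 2, the biopsy falls on days 7 + 14 = 21 to 7 + 21 = 28, which is 14 to 7 days before day 35. Nominally they join. After infusion 1, it falls on days 14–21, a gap of 21 to 14 days, and joins only at exactly 14. At the 14-day edge a slip of one day splits the pair, and the infusion windows allow three.

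**Step 3: size of an NE override**
- Voided response, course 2 given, next valid scan on day 70: 70 − 35 = 35 days late. The durable threshold is 6 × 365.25/12 = 182.6 days, and 35/182.6 = 19%. Responses truly lasting more than 182.6 and up to 182.6 + 35 = 217.6 days from day 35 lose durable status.
- Voided CR, course 2 omitted (as Treatment Plan VI permits), next scan at six months: up to 182.6 − 35 = 147.6 days late, unless an interim assessment was recorded as a response.
- Voided PD: dated late or missed. Day 70 applies only to patients who still receive course 2. Treatment Plan VI makes the second course in Group I conditional on no significant progression.

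**Step 4: chaining**
- Scans alone: gaps are 70 − 35 = 35 and 91 − 70 = 21 days. Both exceed 14, so there are three separate timepoints.
- One extra entry cannot join days 35 and 70: it would have to fall by day 49 (35 + 14) and not before day 56 (70 − 14).
- Two entries can, if the first is on days 42–49, the second on days 56–63, and they are at most 14 days apart. The protocol schedules clinical evaluation at infusions and at least weekly in observation, so exams on such days are expected. Whether they were entered as disease assessments is not stated.

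| Assessments | Gaps (days) | Result as written |
|---|---|---|
| CT PR day 35, exams days 49 and 56, CT PD day 70 | 14, 7, 14 | One PD dated day 35; PR lost, PD 35 days early |
| Same, plus biopsy CR day 28 | 7, 14, 7, 14 | One CR dated day 70; PD deleted |

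**Step 5: ORR.** Each responder lost costs 100/n percentage points in a cohort: 10 points at n = 10 and 5 at n = 20 (assumed sizes). This happens only if no other timepoint shows CR or PR.

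**The case against.** The best defence is that this is a missing clarification. NE sits at the harmless end of the within-modality order, an NE timepoint has no date rule, and SAP 8.2.2 and 8.2.3 call NE not valid, so a sensible programmer would drop it. The protocol's response categories contain no NE, biopsies are taken only if indicated, and nothing shows that an NE biopsy was recorded near an evaluable scan. Lymphoma chaining needs two suitably timed extra entries. SAP section 11 plans no formal hypothesis test.

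Much of this stands. The override is probably unintended and its frequency is unknown. But the wording on validity governs censoring and the death window, and no text repairs the derivation, so two programmers could follow the SAP and reach different responses. SAP 6.3 does cap its laboratory windows, so the lack of a cap for disease assessments is a real gap.

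Four stronger readings may tempt a reader, and the documents do not support them:

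- *Every biopsy after the second infusion joins the day-35 scan.* Visit windows can split them.
- *A voided day-35 PD is always dated 35 days late.* That needs a second course, which is conditional on no significant progression in Group I.
- *The errors are essentially conservative.* A voided PD, or a biopsy CR chained to a later scan PD, favours treatment.
- *In viremia, a day-28 viral response is read as SD.* Table 2 has a column "Priority for Viremia" that ranks blood 1, cohort 171 is "EBV-CTL (Transplant donor derived) Viremia", and blood is "drawn on days 1, 7, 14, 21, and 28 post-T-cell infusion and, monthly thereafter for four months". The first five draws would form one timepoint if each had been rated. No document says that each was. The protocol's viral complete and stable responses also depend on whether EBV LPD develops later, so a single draw cannot establish them.

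**Conclusion.** The concern holds as a defect in a stated rule, and it should be corrected. Taken literally, SAP section 8 lets a rank-1 NE result void an evaluable scan, and it allows successive evaluations to merge without limit.

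The illustrated shifts are 35 days for a response or a PD, and up to about 148 days for a voided CR with no second course and no interim assessment. They rest on back-to-back courses at nominal days, on an NE biopsy falling within 14 days of the scan, and, for chaining, on exams or blood results having been entered as disease assessments.

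The direction can go either way. The documents do not show how often any of this occurred, so no net bias in ORR or the time-to-event endpoints can be claimed.

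**What to change.** 1. Exclude NE results before ranking across modalities. The highest-ranked evaluable modality then decides, and a timepoint is NE only if all its assessments are NE.
2. Limit a timepoint's span so that two scheduled post-course evaluations cannot merge. One way is to start a new timepoint at any scan more than 14 days after the first scan in the current one, treating scans within 14 days of it as one evaluation. The days 35/49/56/70 example then gives a PR (dated day 56 under the latest-date rule) and a separate PD on day 70.
3. Add a sensitivity analysis that dates PD and response from the assessment that determined them. In that example the PR returns to day 35.

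Make the same change to the grouping sentence in SAP 6.3. Do not give each viremia blood draw its own timepoint. ORR counts any CR or PR during the study, so about nine scheduled draws (five plus four monthly) would give as many chances for a transient ten-fold fall to count as a PR.

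The cost is a few lines of SAP text and reprogramming of one derivation. The downsides are slightly more timepoints per subject, hence slightly more chances for a response or a PD to be counted, and an occasional biopsy separated from its scan.

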In addition to physical examinations **and assessments of circulating EBV DNA**, radiological studies, if indicated, including either PET/CT and/or MRI scans, will be obtained at three weeks following each course of three weekly infusions of EBV-specific T-cells, and again at six weeks following the second course of infusions. The size of each lesion will be determined by measuring diameter (length and width) and combine with views. For patients who achieve complete remission, these radiological evaluations will be obtained, if necessary, at six month intervals for one year following the initial infusion, and thereafter as clinically indicated. Patients achieving partial remission or stable disease will be followed at four month intervals following the initial infusion to assess duration of response. Radiological studies will only be performed if necessary. Patients who progress despite two courses of T-cell infusions will be assessed until three weeks following the second infusion, and thereafter as clinically indicated until alternative therapy is initiated.

If indicated, lymph nodes or parenchymal sites of lymphoma will be biopsied 2-3 weeks after the first and/or second dose of EBV-specific T-cells to assess the effects of the infusions on the tissues involved. Biopsied tissues will be examined for histopathologic evidence of lymphoma. Immunohistochemical analyses will be performed to characterize cells infiltrating the biopsied tissues. The presence of cells bearing the EBV antigens EBNA-1, EBNA-2, and LMP-1 will also be assessed. When available, single cell suspensions will be derived from portions of involved tissue and characterized as to immunophenotype, expression of EBV antigens, origin (donor or host) and clonality. Origin will be determined by analysis of separated B- and T lymphocytes for donor or host unique X, Y and/or autosomal polymorphisms by FISH and/or PCR amplified RFLP analyses. Cells will also be analyzed for residual populations of EBV lymphoma cells

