## **VII. Criteria for Diagnosing and Grading Endpoints of Interest**

- 1) Acute toxicities induced by infusions of EBV-specific T-cells will be graded according to the NCI criteria used to grade organ toxicities induced by chemotherapeutic agents (48).
- 2) Allograft rejection episodes developing in organ transplant recipients will be diagnosed, assessed, and managed by the patient's transplant physician, utilizing standard criteria established for the identification and grading of rejection episodes in transplanted kidney, liver, heart or lung allografts (49-51).
- 3) Acute Graft vs. Host Disease will be diagnosed and graded utilizing the IBMTR consensus criteria (47) and the histopathological criteria of Slavin and Woodruff (52). Chronic graft vs. host disease will be diagnosed and graded using the staging criteria developed by Sullivan et al (53).
- 4) The responses of the EBV lymphomas will be identified as complete remission, partial remission, stable disease, or no response with disease progression based on the following criteria:

- Complete remission: Complete resolution of all clinical and radiologic evidence of lymphoma, confirmed by biopsy of affected tissues when indicated, lasting for at least three weeks following completion of a course of cell infusions.
- Partial remission: A 50% or greater reduction in the size of all lymphomatous lesions as determined by CT or MRI based measurements of tumor volume, which is maintained for at least three weeks following completion of a course of cell infusions.
- Stable disease: Less than 50% reduction of lymphomatous lesions without progression at any site maintained for at least 3 weeks following completion of a course of cell infusions.
- No response with disease progression: Progressive enlargement of one or more lymphomatous lesions by three weeks following a course of T-cell infusions.

5) For recipients of HSCTs, and other severely immunocompromised patients who have high and increasing levels of EBV DNA in the blood, without clinical or radiological evidence of tumors, who are treated preemptively with EBV-Specific T cells, a therapeutic response will be defined as:

- Viral - Complete Response: Clearance of EBV without subsequent development of EBV LPD
- Viral - Partial Response: At least a ten-fold decrease in EBV DNA levels
- Viral - Stable Response: Persistence of circulating EBV DNA without development of EBV LPD

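### In viremia cohort 171, a blood result of CR, PR or SD overrides a scan read as PD for new lymphoma at the same timepoint, so the progression is lost

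*SAP*

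**What the plan says.** SAP Section 8 groups investigator disease assessments of all modalities into one timepoint for as long as consecutive gaps are 14 days or less. Two rules then give one response per timepoint.

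- Within a modality the worst result is kept: "If there are multiple assessments with the same modality in the same timepoint assessment, the worst/worse assessment" is the one selected.
- Across modalities, "the overall response for the timepoint assessment will be decided by the rank of the modalities specified in Table 2", with 1 the highest rank. The SAP's own example sets a biopsy PR against a physical-examination CR: "The assessment per biopsy will override that of physical examination for this timepoint assessment".

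Blood is the only row of Table 2 that differs between the two columns. It ranks 4 for non-viremia subjects and 1 under "Priority for Viremia". PET, PET/CT, CT and MRI rank 2 in both columns. Biopsy, pathology and bone marrow rank 1 in both.

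Protocol Section VII (Criteria for Diagnosing and Grading Endpoints of Interest), item 5, defines response for pre-emptively treated patients. Viral complete response is "Clearance of EBV without subsequent development of EBV LPD". Viral stable response also requires that LPD does not develop. Viral progression is persistent EBV DNA followed by LPD. Viral partial response is a ten-fold fall in EBV DNA, with no LPD condition.

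SAP Table 1 marks viremia cohort 171 (transplant donor-derived cells) as enrolled and cohort 71 (tab-cel viremia) as not enrolled. The efficacy layout gives cohort 171 its own column.

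**The concern.** Pre-emptive patients are treated because they are at high risk of EBV lymphoma, and the protocol's definitions make LPD the failure event. An EBV DNA level cannot itself show LPD; tissue, imaging and examination can. Table 2 nevertheless lets blood silence the scan, and Section 8 has no clause that makes new LPD count regardless of the blood result.

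What is at stake is mainly the time-to-event endpoints. The primary definitions of DOR, PFS and TTP (SAP 8.2.2, 8.2.3, 8.2.5) count progression after the last response. A timepoint turned into CR or PR therefore removes its own progression and can also displace an earlier one. The PFS sensitivity analysis based on first progression does not recover the event, because the timepoint is never classed as PD. Durable response rate inherits the longer DOR. ORR is exposed too, but under narrower conditions.

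**Working it through.** There is no planned figure to reproduce; the check applies the stated rules.

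**Step 1: the ranking.** Inputs are both columns of Table 2, the worst-result rule within a modality and the rank rule across modalities. Each row below pairs blood (worst result in the timepoint) with a test read as PD.

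| Blood | Other test | Viremia column | Non-viremia column |
|---|---|---|---|
| CR | CT = PD | CR (rank 1 beats 2) | PD (rank 2 beats 4) |
| PR | CT = PD | PR | PD |
| SD | CT = PD | SD | PD |
| CR, PR or SD | Biopsy = PD | Tie at rank 1, no rule | PD (rank 1 beats 4) |

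PET, PET/CT and MRI behave as CT does. The worst-result rule cannot break the tie in the last row, because it applies only within one modality.

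**Step 2: which blood result is used.** Under Protocol VIII, "heparinized blood (10cc) will be drawn on days 1, 7, 14, 21, and 28 post-T-cell infusion", then monthly for four months. If each draw is a recorded assessment, the gaps are 7 − 1 = 6, then 7, 7 and 7 days. All are 14 or less, so days 1 to 28 form one timepoint. Scans, if indicated, "will be obtained at three weeks following each course of three weekly infusions of EBV-specific T-cells". The protocol does not say which infusion the draw days are counted from. Counted from the first, the third infusion is on day 14 and the scan falls at about 14 + 21 = day 35, which is 7 days after the day-28 draw. Counted from the last, it falls on day 21. Either way the scan joins the chain, and the worst blood result from day 1 onward is used. Blood SD followed by PR, with CT = PD, gives SD. The patient is not a false responder, but the progression is still lost.

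**Step 3: a case that gives a false response.** The first monthly draw falls at about 28 + 30.44 = day 58.4. Suppose it is read CR, and a CT on day 60 is read PD.

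- Day 28 to day 58: 30 days, more than 14, so a new timepoint starts.
- Day 58 to day 60: 2 days, so the draw and the CT are grouped.
- Day 60 to the next monthly draw (about day 89): 29 days, so nothing else joins.

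As written, the timepoint is CR. Section 8 dates a CR to the latest assessment in the group, so the response is dated day 60, the day of the CT that showed progression. Under the non-viremia column the same data give PD.

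**Step 4: effect on ORR.** SAP 8.1 counts any CR or PR during the study. If this patient had responded at an earlier timepoint, ORR would count the patient under either column. The false response matters for ORR only when there was no earlier one.

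**The case against.** Ranking blood first is sensible in itself: these patients have no measurable lesion at baseline, and the protocol's viral response is largely an EBV DNA criterion. Viral partial response carries no LPD condition, so for that category blood-first matches the protocol. A suspicious scan is also not pathologically documented LPD, and biopsy is not outranked by blood. An investigator who knows that LPD has developed might record the blood assessment itself as PD. Only one enrolled cohort is affected, it is reported in its own column, and SAP Section 11 plans no formal hypothesis test on CR.

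These points limit the concern but do not remove it. Biopsy is not outranked, but it is not decisive either. Nothing in the SAP requires the investigator to carry LPD into the blood reading, or says how the viral categories become CR, PR, SD and PD. A ten-fold fall with persistent DNA and new LPD fits both viral partial response and viral progression. Cleared DNA with new LPD is not a viral complete response, yet it does not meet the progression wording either.

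Three stronger readings are tempting and are not supported.

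- A reader might infer that clear EBV DNA on day 21, with a new mass on a scan that day, makes a responder. With each draw counted, days 1 to 28 chain together and the worst blood result applies, so this needs every draw in the chain to be CR or PR.
- A reader might infer from the dense draw schedule that nearly every scan is overridden. Scans are done only if indicated, evaluations are described as approximate and as clinically necessary, and the SAP does not say that each draw is a disease assessment.
- A reader might infer a given inflation of ORR. The size of cohort 171 is not stated, and earlier responses count under any ranking.

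**Conclusion.** The rule is wrong as written for viremia cohort 171 and should be changed. Blood CR, PR or SD masks a scan read as PD for new lymphoma in the same chained timepoint, and a biopsy showing LPD meets blood in an unresolved tie. The consistent effect is a lost progression in PFS, including its first-progression sensitivity analysis, and in TTP and DOR. A false response in ORR is a narrower consequence: the worst blood result in the timepoint must be CR or PR, with no earlier response.

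The number of affected patients cannot be estimated, because the documents give neither the cohort size nor the number of scans. The conclusion assumes that EBV DNA results are entered as blood assessments and are not themselves scored PD when LPD appears. A blacked-out block follows the ORR text in SAP 8.1; nothing is inferred from it. Other cohorts use the non-viremia column and are unaffected.

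**What to change.** Add to SAP Section 8 and as a note to Table 2, for viremia cohorts:

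> Blood sets the viral response only when no tissue, imaging or examination assessment in the same timepoint is read by the investigator as new EBV LPD. If one is, the non-blood modalities decide by their existing rank (tissue over imaging over examination), so a negative biopsy of the lesion still overrides a scan or examination. A resulting PD is dated to the assessment that showed it. If biopsy, pathology or bone marrow ties with blood, the worse result is taken.

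Also state how the protocol's viral categories map to CR, PR, SD and PD, including a ten-fold fall in EBV DNA with new LPD, and cleared DNA with new LPD.

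The dating sentence is a deliberate exception to Section 8, which dates PD to the earliest assessment in the group. With weekly draws chained, the general rule could place a progression seen on a scan as far back as the day-1 draw.

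The cost is a short SAP clause, a mapping table and a re-run for one cohort on data already collected. Response and PFS in that cohort may look slightly less favourable, and a suspicious scan that is read as PD and never biopsied would count as progression.
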